6. DETERMINATION OF PROTOCOL DEVIATIONS

6.1 Definition of Protocol Deviations

CSR reportable PD are defined in accordance with International Conference on Harmonization (ICH) E3 as important PDs related to study inclusion or exclusion criteria, conduct of the trial, subject management or subject assessment resulting in the potential to jeopardize the safety or rights of the trial subjects or the scientific value of the trial. Protocol deviations will be classified as CSR-reportable and non-CSR-reportable and a pre-specified list of protocol deviations will be included in the Protocol Deviation Specification document included in appendix A of this Statistical Analysis Plan.

All reportable PDs will be evaluated before unblinding and most will be classified into the following categories:

- Subject randomized and did not satisfy entry criteria
- Subject developed withdrawal criteria during the study, but was not withdrawn
- Subject received the wrong treatment or incorrect dose
- Subject took an excluded concomitant medication
- Key study procedures missed or performed out of window

CSR reportable PDs will lead to exclusion of the subject or part of the subject's data from at least one analysis set.

The number of subjects in any and by PD category will be summarized by study group and overall. Individual subject listings will be provided in an appendix, sorted by subject and by PD category.

Prior to unblinding, designated study staff will develop a memo that describes the PDs that led to exclusions from analysis sets. This memo will be signed off by at least the Biostatistician and the Clinical Program Medical or Scientific Lead (CPML/CPSL) and will be included in the trial master file.

Prematurely terminating study participation for reasons such as withdrawal of consent or occurrence of adverse events (including death) is not considered as a PD. The missing assessments that should have otherwise been collected for that subject later in the study are also not considered as a PD.

6.2 Determination of Protocol Deviations

A set of listings will be provided to the Clinical Program Medical or Scientific Lead and the Global Clinical Operations Lead for review on an ongoing basis during the study.

The listings will be programmed following the Protocol Deviation Specification list presented in table in [section 7.7](#).

The review will also include protocol deviations captured reported in monitoring reports.

After the review, the Clinical Program Medical or Scientific Lead and the Global Clinical Operation Lead will provide the Biostatistician with:

- An assessment of CSR reportable PDs based on blinded clinical data review.
- An assessment of subjects without PDs (e.g., premature withdrawals due to adverse event, withdrawal of consent) who should be excluded from an analysis set.

6.3 Exclusions of Individual Values for Safety Analysis

Some local and systemic adverse events will be directly measured by the subject and will not be subject to a reconciliation process, even if they are biologically implausible. Therefore these implausible measurements will be removed from the analysis but included in listings. Implausible measurements are summarized in the table below:

Table 6.3-1: Implausible Solicited Adverse Events

Parameter	Implausible measurements
Body temperature	$\leq 33^{\circ}\text{C}$ or $\geq 42^{\circ}\text{C}$
Erythema	Measurements: ≥ 900 mm or < 0 mm
Induration	Measurements: ≥ 500 mm or < 0 mm
Ecchymosis	Measurements: ≥ 500 mm or < 0 mm

7. ANALYSIS SETS

7.1 All Enrolled Set

All screened subjects who provide informed consent and provide demographic and/or other baseline screening measurements, receive a subject ID, regardless of the subject's randomization and vaccination status in the trial.

Demography and baseline characteristics tables will be produced on the All Enrolled Set, Full Analysis set, Per Protocol Set and Overall Safety Set.

7.2 Exposed Set

All subjects in the All Enrolled Set who received a study vaccination.

7.3 Full Analysis Set (FAS), Efficacy / Immunogenicity Set

Full Analysis Set (FAS)

All subjects in the All Enrolled Set who are randomized and received a study vaccination (demography)

Full Analysis Set Efficacy:

All subjects in the All Enrolled Set who are randomized and received a study vaccination, are under observation for at least 21 days post-vaccination and provide efficacy data.

Full Analysis Set Immunogenicity:

A randomly selected sample of 1,702 subjects including subjects from both treatment arms (1,362 Aqiv; 340 Boostrix), in the All Enrolled Set who are randomized, received a study vaccination, and provide immunogenicity data at Days 1 and 22, see [Section 4.1](#).

See [section 4.1](#) for details on how to handle subjects randomized in the wrong stratum.

If a subject is unblinded during the study, he/she will be included in the FAS.

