8.3.4 Full Analysis Set (FAS) Efficacy/Immunogenicity Set

Full Analysis Set Efficacy (primary and secondary efficacy objectives)

All subjects in the All Enrolled Set who are randomized and receive a study vaccination, are under observation for at least 21 days post-vaccination and provide efficacy data.

Full Analysis Set Immunogenicity

A randomly selected sample of 1,702 subjects including subjects from both treatment arms (1,362 aQIV; 340 Boostrix), in the All Enroled Set who are randomized, receive a study vaccination and provide blood specimens before and after vaccination. Several FASs for all relevant immunogenicity endpoints will be detailed in the SAP.

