2.1.2 Primary Efficacy Endpoints

The primary efficacy endpoint is the time of first-occurrence of RT-PCR-confirmed influenza due to A (H1N1 and H3N2) or either B lineage due to any strain of influenza regardless of antigenic match to the strains selected for the seasonal vaccine from 21 through 180 days after vaccination or end of the influenza season, whichever is longer.

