2.2.3 Secondary Efficacy Endpoints

In addition to the primary efficacy endpoint, additional endpoints for the secondary efficacy objectives are sought, based on antigenic match of culture isolated influenza to the strains of virus contained in the seasonal vaccine.

The secondary efficacy endpoints are the time to first occurrence of culture-confirmed influenza, due to

- Influenza strains regardless of antigenic match (Secondary Efficacy Objectives 2)
- Antigenically unmatched strains of influenza virus (Secondary Efficacy Objective 3).

selected for the seasonal vaccine from Day 21 to Day 180 after vaccination or the end of the influenza season, whichever is longer.

and

- Time to first occurrence of RT-PCR-confirmed influenza due to any strain of influenza regardless of antigenic match from 7 days to 180 days after vaccination or at the end of influenza season, whichever is longer (Secondary Efficacy Objective 4).

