8.2.3 Efficacy Data

Efficacy data will be analyzed using both the FAS (Efficacy) and the PPS, irrespective of the difference in size between the two analysis sets.

The following algorithm will be applied:

1. If less than 20% of subjects are without efficacy data (e.g., ILI swabs collected without any RT-PCR assessment record), then the analyses will be run on FAS and PPS and no further statistical evaluation will be performed.
2. If observations are missing for 20% or more of subjects, the missing mechanism will be analyzed with vaccine group as a categorical variable and a newly created variable describing the missing information as dependent variable (1=efficacy record present; 0=efficacy record not present). It will be tested, by chi-square test, if the proportion of missing observations/subjects varies significantly between vaccine groups. If the difference is significant with $P < 0.05$ then a sensitivity analysis will be performed of the primary efficacy analysis imputing randomly x% (from 0% to 100% in 10% increments) of missing data as PCR-confirmed cases.

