12.2 Secondary Objectives Analysis

Hypotheses for testing secondary objectives are formulated in the similar way as for the primary efficacy objective. If an interim analysis is performed and the trial doesn't stop, then all the subsequent secondary analysis will be tested at a reduced alpha level, i.e. what's left from the interim analysis. The confidence interval will be higher than 95% instead of 95% at the final analysis.

All secondary efficacy objectives will be evaluated based on the Efficacy FAS, but analysis for the key secondary objective will be also repeated based on Efficacy PPS. For non-key secondary objectives, if the percentage of vaccinated subject excluded from the FAS is greater than 5%, a secondary analysis based on the PPS will be performed to complement the FAS.

Similarly to the primary efficacy objectives, a Cox PH model will be used to estimate absolute vaccine efficacy VE for each secondary objective 1-4.

Criteria for evaluation : if the lower limit of the 95% two-sided confidence interval for VE estimate is greater than 40% then the secondary efficacy objectives will be demonstrated.

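### Early efficacy (secondary objective 4) counts influenza from Day 7, but its analysis set requires 21 days of observation, so subjects who leave between Day 7 and Day 21 are deleted with their events or risk time

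*SAP*

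**What the plan says.** **Window.** SAP 2.2.3 defines the early-efficacy endpoint as first RT-PCR-confirmed influenza "regardless of antigenic match from 7 days to 180 days after vaccination or at the end of influenza season", whichever is longer. It calls this Secondary Efficacy Objective 4; the same objective is item 3 in the list in SAP 2.2.2 and item 4 in protocol 2.2. The primary endpoint (SAP 2.1.2) runs "from 21 through 180 days after vaccination or end of the influenza season, whichever is longer".

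**Analysis set.** SAP 12.2 states: "All secondary efficacy objectives will be evaluated based on the Efficacy FAS". Protocol 8.4.3.2.2 agrees. Under SAP 7.3, members of that set are randomised, vaccinated subjects who "are under observation for at least 21 days post-vaccination and provide efficacy data". Protocol 8.3.4 gives the same rule and labels the set as serving both primary and secondary efficacy objectives. The PPS is a subset of this FAS (SAP 7.4), and SAP 7.6 lists no other set.

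**Censoring.** SAP 12.1 right-censors subjects who drop out during observation. SAP 12.2 carries a similar Cox model over to objectives 1 to 4.

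**Efficacy data.** SAP 7.3 does not define the term. The missing-data rule in SAP 8.2.3 gives one example of subjects lacking such data: "ILI swabs collected without any RT-PCR assessment record".

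**The concern.** A 21-day observation requirement suits a window that opens at Day 21. It does not suit one that opens at Day 7, because membership then depends on what happens during the first 14 days of the risk period. Two kinds of subject are mishandled:

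- Someone with confirmed influenza on Day 12 who dies or withdraws on Day 18 is deleted along with the event.
- Someone without influenza who leaves on Day 15 is deleted, where the plan's own censoring rule would keep the risk time up to that day.

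Days 7 to 20 are the only days that distinguish objective 4 from the primary endpoint, so the selection acts on exactly the part of follow-up that the objective was added to capture. If leaving early were related to influenza and differed by arm, the early-efficacy estimate would be biased.

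**Working it through.** **Inputs from the documents** (SAP 5, protocol 8.5): attack rates 3.5% (comparator) and 1.4% (aQIV); 4,860 evaluable subjects per group; 238 events; 10,692 randomised, 5,346 per group; 10% drop-out.

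**Assumptions not in the documents:** drop-out uniform over 366 or 180 days; the Day 21–180 hazard also holds on Days 7–20; the share of early cases who leave before Day 21.

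1. *Plan's figure.* 4,860 × (0.035 + 0.014) = 238.1 events, which matches 238. The documents give no event count or power for early efficacy.

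2. *Expected early cases.* Days 7–20 are 14 days and Days 21–180 are 160 days.
   - Comparator: 4,860 × 0.035 × 14/160 = 14.9
   - aQIV: 4,860 × 0.014 × 14/160 = 6.0
   - Sum 20.8, giving 238.1 + 20.8 = 259.0 cases from Day 7, of which 20.8/259.0 = 8.0% are early.

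3. *Subjects at risk at Day 7 whom the rule removes.*
   - Over 366 days: 10,692 × 0.10 × 14/366 = 40.9 (0.4%)
   - Over 180 days: 10,692 × 0.10 × 14/180 = 83.2 (0.8%)

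   Both lie far below the 20% threshold in SAP 8.2.3 (0.20 × 10,692 = 2,138), so the existing missing-data check would not notice them.

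4. *Cases lost if leaving is unrelated to influenza.* A leaver is at risk for 7 of the 14 days on average.
   - Over 180 days: 5,346 × 0.10 × 14/180 × (0.035 + 0.014) × 7/160 = 0.09
   - Over 366 days: the same with 14/366 = 0.04

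5. *Cases lost if leaving is linked to influenza.* If 1% to 5% of early cases leave before Day 21: 20.8 × 0.01 = 0.2 to 20.8 × 0.05 = 1.0.

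6. *Effect on estimated VE.* Take true VE as 60% throughout, approximate the hazard ratio by the ratio of retained cases, and let q_C and q_A be the shares of early cases lost in the comparator and aQIV arms. Cases from Day 21 are 4,860 × 0.014 = 68.04 (aQIV) and 4,860 × 0.035 = 170.1 (comparator).

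   VE = 1 − [68.04 + 5.95(1 − q_A)] / [170.1 + 14.88(1 − q_C)]

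| q_C | q_A | VE |
|---|---|---|
| equal | equal | 60.0% |
| 5% | 15% | 1 − 73.10/184.24 = 60.3% |
| 15% | 5% | 1 − 73.70/182.75 = 59.7% |
| 0% | 100% | 1 − 68.04/184.98 = 63.2% |
| 100% | 0% | 1 − 73.99/170.1 = 56.5% |

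   The last two rows are outer bounds, not plausible scenarios. If VE on Days 7–20 were zero, the Day-7 VE would be 1 − (68.04 + 14.88)/184.98 = 55.2%. An equal 10% loss of early cases would then give 1 − 81.44/183.50 = 55.6%, so equal loss also shifts the estimate slightly once early VE differs from later VE.

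**The case against.** The strongest reply is that this hardly matters. The rule is the same in both observer-blinded arms, an early case who stays to Day 21 is kept, and the expected loss is a fraction of a case. Protocol 8.2.2.2 also says that secondary efficacy objectives other than the key one are not tested for success. All of that stands and limits the severity. It does not make the set right for the objective. Nor is the status of the objective entirely settled: SAP 12.2 attaches a 40% lower-limit criterion to the secondary efficacy objectives without restricting it to the key one, which should be reconciled with the protocol.

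Three stronger readings are tempting, and the documents do not support them.

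- *Immortal-time bias.* A reader might call the first 14 days immortal time. No time is misallocated to one arm; the restriction applies to both. Post-baseline selection is the accurate description.
- *The FAS selects on swab success.* A reader might combine the efficacy-data condition with the example in SAP 8.2.3 and conclude that a failed swab removes a subject. That example sits in a missing-data rule and can equally mean that the subject stays in the FAS with a missing result. Subjects without an ILI have no swab, so the term cannot require a swab result. Swabs are also cultured (protocol 7.2), and protocol 8.1.1.2 accepts RT-PCR or culture confirmation. What stands is that the term is undefined. SAP 7.5 does settle the parallel question for unsolicited safety data, where a record of no event counts as data.
- *The primary analysis is affected.* Not by the 21-day rule: anyone gone before Day 21 contributes no time to a window opening then.

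**Conclusion.** The mismatch is explicit in both documents and needs no interpretation: objective 4 opens at Day 7, and the only set available for it requires observation to Day 21. Following the plan as written applies the wrong risk set to a pre-specified, non-key secondary objective.

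The effect should be small. The subject and case counts above rest on uniform drop-out and a constant hazard. Front-loaded drop-out, or vaccination closer to peak circulation, would raise them; a window extending past Day 180 would lower the early case count. A visible bias in VE needs leaving that is linked to influenza and differs between arms. Even the assumed 5% versus 15% split of early-case losses moves VE by only about 0.3 points.

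This is a low-severity correction, worth making because it is certain and cheap. The undefined efficacy-data condition is a separate clarification and not evidence of outcome-linked exclusion.

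**What to change.** **Main change.** In protocol 8.3.4 and SAP 7.3, state that for objective 4 the Efficacy FAS is all randomised, vaccinated subjects under observation at Day 7, with risk time from Day 7 to event, last contact or end of window. Any PPS analysis of this objective should be drawn from that set. The 21-day requirement can stay for the objectives whose window opens at Day 21.

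**Secondary clarification.** State in the same sections that the efficacy-data condition is met by any ILI surveillance follow-up in the relevant window. A subject whose swab lacks an RT-PCR result then stays in the FAS and is handled under the missing-data rule in protocol 8.4.2.2.3 and SAP 8.2.3. Censoring such a subject at that ILI is not advised as the main approach, because it removes people when they are most likely to be cases. Unlike the main change, this clarification could alter the primary risk set if the current wording would have excluded such subjects, so it should be settled before unblinding.

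**Cost.** A few sentences and one additional population flag. No new data are needed: surveillance and swabbing already run from Day 1 (protocol 3.5, 5.3.3 and 7.2).

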7.4 Per Protocol Set (PPS)

All subjects in the FAS Efficacy / Immunogenicity who:

- Correctly received the vaccine (i.e., receive the vaccine to which the subjects is randomized to receive).

- Had no CSR-reportable PD leading to exclusion (see [section 6.2](#)) as defined prior to unblinding or analysis.
- Are not excluded due to other reasons defined prior to unblinding (see [section 6.2](#))

In case of vaccination error, the subject is excluded from the PPS. If a subject receives a vaccine, labelled for another subject but the same as the one the subject was randomized to, the subject will not be removed from the PPS.

If a subject received the correct study vaccine (dose, batch) but from another ongoing study at the site, then the subject should be excluded from the PPS.

See [section 4.1](#) for details on how to handle subjects randomized in the wrong stratum.

If a subject is unblinded during the study (except for possible SUSARs), he/she will be excluded from the PPS.

Primary vaccine efficacy analyses will be based on the Efficacy/immunogenicity FAS, and repeated, as a sensitivity analysis, on the Efficacy/immunogenicity PPS.

7.5 Safety Set

Solicited Safety Set

All designated subjects (i.e., a sample of 1053 subject from each treatment arm) in the Exposed Set, with solicited safety assessments beyond 30 minutes (e.g., use—or lack of use—of analgesics/antipyretics).

Unsolicited Safety Set

All subjects in the Exposed Set with unsolicited adverse event data.

A record of safety assessment performed at a specific time point, with confirmation of no AE, is considered as adverse event data hence subject is to be included.

Overall Safety Set

All subjects who are in the solicited safety set and/or in the unsolicited safety set.

Subjects providing only 30 minute post-vaccination safety data will be reported separately in a 30 minute post-vaccination safety analysis and excluded from all other safety analysis.

In case of vaccination error, subjects will be analyzed as “treated” (i.e., according to the vaccine a subject receives, rather than the vaccine to which the subject is randomized).

If a subject received the correct study vaccine (dose, batch) but from another ongoing study at the site then the subject’s safety data should be included in the safety analyses.

In case a subject is randomized in the wrong stratum:

- Subject will be reassigned to the correct stratum for solicited and unsolicited safety analyses.

If a subject is unblinded during the study, he/she will be included in all the safety analyses.

7.6 Other Analysis Set

None

7.7 Overview of Analysis Sets by PD

See Protocol Deviation Specification document included in Appendix A.

8. GENERAL ISSUES FOR STATISTICAL ANALYSES

8.1 Adjustment for Covariates

The estimate of the hazard ratio and the respective estimate for relative vaccine efficacy (rVE) and pertaining 2-sided 95% confidence intervals will be calculated based on the Cox proportional hazards model with vaccine group as the main effect. Randomization stratifying factors (ie, by age (cohorts 65 to 74 years and 75 years and above), study site, and risk for complications from influenza (assessment score < 50 or ≥ 50) will be modelled as random effects as suggested by [Kahan and Morris \(2012\)](#). In case of computational difficulties due to small number of events (for example, in a subgroup analysis) an unadjusted hazard ratio will be estimated and reported. Small sites (<30 subjects) will be grouped within country.

The log-transformed antibody titer at day 1, Day 22, Day 181 and Day 366 will be analyzed, in key analyses, using an Analysis of Covariance (ANCOVA) model which includes the site effect (with small sites grouped within country), an effect defined by the log-transformed pre-vaccination antibody titer, age stratification and comorbidity (<50, ≥ 50). Summary tables will show both adjusted and unadjusted GMTs and adjusted and unadjusted ratios of GMTs for each vaccine group, except for subgroup analyzes which will present unadjusted estimates only.

Binary data tables will show unadjusted percentages.

8.2 Handling of Dropouts, Missing Data

First-line analyses will be without missing values.

To minimize the effect of dropouts and missing data the study period will be divided into time intervals for statistical analysis of safety, immunogenicity, and efficacy.

8.2.1 Safety Data

For unsolicited adverse events, the entire study period will be divided into the following intervals: Day 1 – Day 22; Day 23 – Day 181; Day 182 – Day 366, and Day 1 – Day 366.

For solicited adverse events, the solicited study period 30 min – Day 7 will be divided into: 30 min, 6h – Day 3, Day 4 – Day 7, and overall interval: 6h – Day 7.

No imputation of missing solicited or unsolicited AEs will be used. The percentage of subjects with missing solicited AE assessments (e.g. missing Patient Diary) and missing Safety Phone Calls or Safety Assessments will be reported for each time period.

8.2.2 Immunogenicity Data

Missing immunogenicity values are considered missing completely at random (MCAR) and therefore will not contain information that impact the result of the analysis (i.e., not informative). Imputation methods will therefore not be used. The secondary objectives will be analyzed using the FAS (immunogenicity). If the percentage of vaccinated subject excluded from the FAS (immunogenicity) is greater than 5%, a secondary analysis based on the PPS will be performed to complement the FAS.

8.2.3 Efficacy Data

Efficacy data will be analyzed using both the FAS (Efficacy) and the PPS, irrespective of the difference in size between the two analysis sets.

The following algorithm will be applied:

1. If less than 20% of subjects are without efficacy data (e.g., ILI swabs collected without any RT-PCR assessment record), then the analyses will be run on FAS and PPS and no further statistical evaluation will be performed.
2. If observations are missing for 20% or more of subjects, the missing mechanism will be analyzed with vaccine group as a categorical variable and a newly created variable describing the missing information as dependent variable (1=efficacy record present; 0=efficacy record not present). It will be tested, by chi-square test, if the proportion of missing observations/subjects varies significantly between vaccine groups. If the difference is significant with $P < 0.05$ then a sensitivity analysis will be performed of the primary efficacy analysis imputing randomly x% (from 0% to 100% in 10% increments) of missing data as PCR-confirmed cases.

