5.3.3 Active Influenza Surveillance Phone Calls/Messages

Active surveillance for ILI for each subject will be conducted weekly either via telephone contacts or message from Day 1 to Day 181, or until the end of the influenza season, whichever is longer. The subject will be asked via phone/message a scripted set of questions to determine if symptoms of ILI are present. The purpose of the phone call/message is to trigger a clinic (or home) visit and a NP swab sample collection if ILI symptoms are present. Should ILI symptoms be present, the subject will also be reminded to complete the ILI booklet. Neither phone calls nor message are intended to collect any clinical data. Site personnel's follow up on all cases meeting primary protocol-defined ILI criteria is to be documented in the subject's source records and monitored in order to ensure that all subjects with ILI symptoms are scheduled for the NP swab sample collection visit as soon as possible within 3, but up to 6, days after the first day of onset of ILI symptoms. Data collected will be monitored by the study monitors in order to ensure adherence to the study protocol.

The subject will also be reminded to contact the site immediately if he or she experiences symptoms meeting primary protocol-defined ILI criteria to have a NP swab collected for evaluation of the presence of influenza virus. If anti-viral medications (e.g. neuraminidase inhibitors) are prescribed it is recommended that an NP swab be obtained prior to the first dose.

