7.2 Efficacy Assessment

Confirmation of influenza infection by RT-PCR or culture from a nasopharyngeal swab sample is necessary for the efficacy assessment in the study. Nasopharyngeal swab retrieval will be initiated after primary protocol-defined ILI has been identified. Primary protocol-defined ILI can occur at any time during the study and will be evaluated in each subject from Visit 1 (Day 1) through Study Termination. ILI symptoms will be captured during study visits. The ILI onset day is defined as the first day that the subject meets the primary protocol-defined ILI. The end date is defined as the date the last symptom resolves. A new ILI episode will only be taken into account after resolution of the previous one, as judged by the investigator (suggested interval between two ILI episodes is 14 symptom-free days).

Subjects with primary protocol defined ILI will have a NP swab collected for evaluation of the presence of influenza virus. NP swabs should be targeted for collection within 3 days from the ILI onset to ensure optimal viral yield, however samples will be accepted if collected up to 6 days following the day of ILI onset. NP swabs will not be taken beyond a total of 7 days (6 days following onset of ILI) as the level of virus detectable beyond this period can be negligible, particularly for influenza A.

All NP swabs collected from subjects with ILI will be shipped under pre-specified conditions in viral transport media to a qualified lab and stored for analysis for influenza.

NP swabs will be analyzed by RT-PCR and placed into culture. The result of the RT-PCR assay will be the presence or absence of influenza virus. The viral culture will be used for the purpose of viral expansion to enable phenotypic characterization of the influenza virus (e.g. antigenic match). Testing will be conducted by a designated laboratory in a blinded manner towards the treatment arm. Please see the Protocol Ancillary Document for name(s) and details.

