5. SAMPLE SIZE AND POWER CONSIDERATIONS

Efficacy objectives:

Sample size and power consideration for the aQIV efficacy objective is based on criteria for demonstrating efficacy in placebo controlled studies provided in CBER guidance, specifically that the study should be powered to assess the lower bound of the two-sided 95% CI of vaccine effectiveness, anticipated to be substantially above zero. This study is planned using a group sequential design. The power of Cox Regression which is planned to be used for analysis is dependent on the overall number of influenza cases, so the sample sizes on number of subjects described in this section is provided more for operational reasons. Additional information on the planning of number of subjects that may need to be enrolled if it is decided to continue enrolment after interim analyses is described in [Section 8.6](#).

For the primary efficacy objective: with 1-sided alpha of 2.5% and assuming an attack rate of influenza of 3.5% among subjects enrolled in the non-influenza comparator group and 1.4% among the aQIV group, i.e. 60% assumed vaccine efficacy for aQIV, 238 events (i.e. 4,860 subjects per group under the assumed ERs) are needed with 86.5% power to show the absolute efficacy of aQIV versus non-influenza comparator, in preventing first occurrence RT-PCR-confirmed influenza A and/or B, due to any strain of influenza regardless of antigenic match to the strains in aQIV, in subjects ≥ 65 years of age, using a margin of 40% for lower bound of the CI for absolute vaccine efficacy.

For the first secondary efficacy objective: with a group vaccine efficacy of 65% but expecting conservatively reduced event rates of influenza cases due to matched strains of 2.5% among subjects in the non-influenza comparator group and 0.9% among the aQIV group then 144 events has estimated power approximately 88.5% to show the absolute efficacy of aQIV versus non-influenza comparator, using a margin of 40% for lower bound of the CI.

Assuming a drop-out rate of 10%, approximately 10,692 subjects ≥ 65 years, 5,346 per vaccine group will be randomized to receive either aQIV or non-influenza comparator (Boostrix®) in a 1:1 allocation ratio, stratifying by age (≥ 65 to 74 and ≥ 75 years of age), study site and by low vs high risk of influenza complications (score < 50 vs ≥ 50).

Immunogenicity objective:

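### The only missing-outcome sensitivity analysis of the primary endpoint is triggered by conditions that do not track the threat to the 40% limit, and where it does run it is uninformative

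*SAP*

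**What the plan says.** SAP 8.2.3 and Protocol 8.4.2.2.3 carry the same two-step rule.

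- **First condition.** The trigger is a share of subjects: "If less than 20% of subjects are without efficacy data (e.g., ILI swabs collected without any RT-PCR assessment record"). Under that threshold the plan goes no further, in these words: "then the analyses will be run on FAS and PPS and no further statistical evaluation will be performed".
- **Second condition.** At 20% or more, a chi-square test compares the proportion missing between arms. Only if P<0.05 is the primary analysis repeated, "imputing randomly x% (from 0% to 100% in 10% increments) of missing data as PCR-confirmed cases". One x is named, with no separate rate by arm.

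Nothing else in the plan resolves a missing primary outcome:

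- Drop-outs are censored (SAP 12.1).
- The PPS repeat uses a subset of the FAS (SAP 7.4), and the crude VE estimate (SAP 12.1) imputes nothing.
- SAP 6.1 lists a deviation category, "Key study procedures missed or performed out of window", summarized by study group. The detailed classification is in Appendix A, which is not in the text reviewed.

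The Efficacy FAS takes vaccinated, randomized subjects who "are under observation for at least 21 days post-vaccination and provide efficacy data" (Protocol 8.3.4; same wording in SAP 7.3). Missing efficacy data is described only by an example.

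**The concern.** The primary objective succeeds if the lower confidence limit of VE exceeds 40%. Unresolved results are foreseeable. A swab may yield no valid assay result, and Protocol 7.2 sets a cut-off: "NP swabs will not be taken beyond a total of 7 days (6 days following onset of ILI").

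Whether such results matter depends on how many true cases they hide and how those cases divide between arms. The first condition measures neither: it is a share of subjects, with the denominator not stated. The second compares only how many are missing per arm, so it never opens when missingness is balanced, even if efficacy among the unresolved is lower.

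Below 20% missing, or with balanced arms, the plan gives readers no estimate of how the unresolved results could affect the success decision. A result well clear of 40% and one close to it would be reported alike.

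**Working it through.** **Inputs.** From SAP section 5: the design is sized "with 1-sided alpha of 2.5% and assuming an attack rate of influenza of 3.5"% in the comparator group and 1.4% with aQIV (VE 60%), 238 events, 4,860 evaluable per group, 86.5% power, 40% margin. From SAP 14.1, Table 1: efficacy boundaries 0.00625 and 0.02275, futility boundary 0.35022, interim at 119 events. Assumed, because the documents give none: the share of subjects unresolved, positivity among them, and VE among them.

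**Plan's own figure.** Take the effect as log(0.4/0.6), information 238/4 = 59.5, and the Table 1 boundaries with binding futility. Two-stage power is then 86.45%, which reproduces the stated 86.5%.

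**Expected cases.** 4,860 × 1.4% = 68 and 4,860 × 3.5% = 170.

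**Lower limit.** With a aQIV cases, b comparator cases and equal denominators, an unadjusted Wald approximation to the Cox result is

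LL = 1 − (a/b) × exp(1.96 × √(1/a + 1/b)).

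- Planned, 68 vs 170: 1 − 0.400 × exp(1.96 × 0.1435) = 47.0%.
- Add 22 per arm, 90 vs 192: 1 − 0.469 × exp(1.96 × 0.1277) = 39.8%, with VE 53.1%. Adding 21 per arm gives 40.1%.
- At the Table 1 final boundary (0.02275 one-sided) the planned limit is 46.7% and 21 per arm are enough.

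The 44 added cases are 44/238 = 18.5% of planned events and 44/9,720 = 0.45% of subjects. The first condition needs 0.20 × 9,720 = 1,944 subjects (2,138 if taken from 10,692 randomized).

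**Dependence on VE among the unresolved.** Add k comparator cases and (1 − VE) × k aQIV cases. The limit reaches 40% at:

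- VE 0%: k = 21.3 in each arm.
- VE 20%: 29.7 aQIV plus 37.1 comparator.
- VE 30%: 41.8 plus 59.7.
- VE 50%: never. At 60% the limit rises slightly; for example, 2% unresolved with 8% and 20% positivity gives 47.8%.

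**Dependence on the share unresolved, zero efficacy among them.** The flip positivity is 21.3 divided by the number unresolved per arm.

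| Unresolved per arm | Number | Positivity in both arms that takes LL to 40% | LL at 20% positivity in both arms |
|---|---|---|---|
| 2% | 97.2 | about 22% | 40.5% |
| 1% | 48.6 | about 44% | 43.6% |
| 0.5% | 24.3 | about 88% | 45.2% |

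**Dependence on observed VE, 238 cases.** At 55% (73.9 vs 164.1) the limit starts at 40.8% and 3 zero-efficacy cases per arm take it below 40%. At 65% it takes 41.9 per arm and at 70% it takes 64.5. With 2% unresolved that is 43% and 66% positivity.

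**Other reading of the denominator.** If 20% means a share of swabbed subjects, 19.9% unresolved at the same overall positivity hides 238 × 0.199/0.801 = 59 cases. The limit is then 37.7% at VE 0% among them, 40.7% at 20%, 44.2% at 40% and 48.6% at 60%.

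**When both conditions are met.** With 1,944 missing, P<0.05 first occurs at a difference of 78, that is 1,011 vs 933 (P=0.048, no continuity correction). At x = 10%, applied alike in both arms to a 68 vs 170 result:

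- More missing in aQIV: 169.1 vs 263.3 cases, LL = 1 − 0.642 × exp(1.96 × 0.0985) = 22.1%.
- More missing in the comparator: 161.3 vs 271.1 cases, LL = 1 − 0.595 × exp(1.96 × 0.0994) = 27.7%.

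A single rate makes efficacy among the missing close to zero by construction. A planned result therefore fails at the first nonzero step, whatever the truth.

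**The case against.** The strongest reply is that nothing suggests lower efficacy among the unresolved. The trial is observer-blind, testing is blinded to arm, and the swab trigger is the same in both arms. Missingness unrelated to outcome within arm and balanced between arms does not bias the hazard ratio. This stands. A reader might infer that the planned estimate is biased or that the rule hides a failing result; the documents support neither.

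Second, the tipping scenarios are demanding when few results are unresolved. At 0.5% unresolved, even zero efficacy would need about 88% positivity. The example at 55% observed VE starts less than one point above the limit. This also stands, and it is why the share is shown as a range. But a tipping-point table is exactly what would show such robustness.

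Third, all swabs are also cultured, and culture-confirmed influenza of any strain is a planned secondary analysis. That is partial cover: a swab without an RT-PCR record may have a culture result, but a secondary endpoint does not show what unresolved results do to the primary limit. Counting deviations by arm does not show it either.

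Finally, the FAS wording might be taken to exclude subjects with an unresolved swab. That is one possible reading only. It calls for clarification and carries none of the magnitude here.

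**Conclusion.** The point holds as a robustness gap that should be closed. The only missing-outcome analysis of the primary endpoint depends on two conditions that do not measure influence on the 40% decision. It is silent where it could inform, and its outcome is largely fixed in advance where it runs.

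From a planned result, zero efficacy among 22 unresolved true cases per arm would overturn success, far below the 20% threshold on an all-subjects reading. With the planned 60% VE among them it would not. An observed VE of 65-70% leaves much more room. All of this rests on assumed shares, positivity and VE among the unresolved, and on an unadjusted approximation to the Cox limit.

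**What to change.** In SAP 8.2.3, replace both conditions with a tipping-point table that is always reported for the primary analysis. Vary positivity among unresolved subjects separately by arm, include the same-VE and zero-efficacy scenarios, and read the table against the positivity observed among assayed swabs.

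Define missing as, at least, an in-window ILI meeting the primary definition with no valid RT-PCR result, and show any culture result for those swabs. Add ILIs with no swab or a late swab only where recorded data identify them. This will be limited, since Protocol 5.3.3 says of surveillance contacts: "Neither phone calls nor message are intended to collect any clinical data". Confirm in SAP 7.3 that all these subjects stay in the Efficacy FAS.

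Align Protocol 8.3.4 and 8.4.2.2.3 at the next amendment.

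The cost is SAP wording and one table, produced even when missingness is small. The estimator, alpha, sample size and conduct do not change. The Protocol alignment needs amendment approval under Protocol 13.4, so it is best not done on its own.
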